9.2 Withdrawal of informed consent and exercise of participant's data privacy rights

Patients may voluntarily withdraw consent to participate in the study for any reason at any time. Withdrawal of consent (WoC) occurs only when a patient:

• Explicitly requests to stop use of their data,

and

No longer wishes to receive study treatment,

and

Does not want any further visits or assessments (including further study-related contacts)

Withdrawal of consent impacts ability to further contact the patient, collect follow-up data (e.g. to respond to data queries) and potentially other restrictions. It is therefore very important to ensure accurate recording of withdrawal vs. discontinuation based on the protocol definitions of these terms.

In this situation, the Investigator should make a reasonable effort (e.g. telephone, e-mail, letter) to understand the primary reason for the patient's decision to withdraw his/her consent/exercise data privacy rights and record this information. The Investigator shall clearly document if the patient has withdrawn his/her consent for the use of data in addition to a study discontinuation.

Study treatment must be discontinued and no further assessments conducted, and the data that would have been collected at subsequent visits will be considered missing.

Further attempts to contact the patient are not allowed unless safety findings require communicating or follow-up.

If the patient agrees, a final evaluation at the time of the patient's withdrawal of consent/exercise data privacy rights should be made as detailed in the assessment table.

Further details on withdrawal of consent or the exercise of patients' data privacy rights are included in the corresponding informed consent form.

Page 45 of 63

9.2.1 Lost to follow-up

For patients whose status is unclear because they fail to appear for study visits or fail to respond to any site attempts to contact them without stating an intention to discontinue from study treatment or discontinue from study or withdraw consent (or exercise other participants' data privacy rights), the Investigator must show "due diligence" by documenting in the source documents steps taken to contact the patient, e.g. dates of telephone calls, registered letters, etc. A patient should not be considered as lost to follow-up until due diligence has been completed or until the end of the study.

9.2.2 Early study termination by the sponsor

The study can be terminated by Novartis at any time.

Reasons for early termination (but not limited to):

- Unexpected, significant, or unacceptable safety risk to patients enrolled in the study
- Decision based on recommendations from applicable board(s) after review of safety and efficacy data
- Discontinuation of study treatment development

In taking the decision to terminate, Novartis will always consider patient welfare and safety. Should early termination be necessary, patients must be seen as soon as possible and treated as a prematurely withdrawn patient. The investigator may be informed of additional procedures to be followed in order to ensure that adequate consideration is given to the protection of the patient's interests. The study is only conducted in China, the Investigator or Novartis depending on local regulation will be responsible for informing IRBs/IECs of the early termination of the trial.

9.3 Study completion and post-study treatment

Study completion is defined as when the last patient finishes their Study Completion visit and any repeat assessments associated with this visit have been documented and followed-up appropriately by the Investigator or, in the event of an early study termination decision, the date of that decision (e.g. Each patient will be required to complete the study in its entirety and thereafter no further study treatment will be made available to them).

All treated patients should have a safety follow-up call conducted 30 days after last administration of study treatment. The information collected is kept as source documentation. All SAEs reported during this time period must be reported as described in Section 10.1.3. Documentation of attempts to contact the patient should be recorded in the source documentation.

Continuing care should be provided by the investigator and/or referring physician based on patient availability for follow-up. This care may include:

Enrollment in an extension study, if any

10 Safety monitoring and reporting

The definitions of adverse events (AEs) and serious adverse events (SAEs) can be found in Section 10.1.

The Investigator and any qualified designees are responsible for detecting, documenting, and recording events that meet the definition of an AE or SAE and remain responsible for following up.

The method of recording, evaluating, and assessing causality of AEs and SAEs and the procedures for completing and transmitting SAE reports are provided in Section 10.1.3.

10.1 Definition of adverse events and reporting requirements

10.1.1 Adverse events

An AE is any untoward medical occurrence (e.g., any unfavorable and unintended sign [including abnormal laboratory findings], symptom or disease) in a clinical investigation participant after providing written informed consent for participation in the study. Therefore, an AE may or may not be temporally or causally associated with the use of a medicinal (investigational) product.

The investigator has the responsibility for managing the safety of individual participant and identifying AEs.

Novartis qualified medical personnel will be readily available to advise on trial related medical questions or problems.

The occurrence of AEs must be sought by non-directive questioning of the patient at each visit during the study. Adverse events also may be detected when they are volunteered by the patient during or between visits or through physical examination findings, laboratory test findings, or other assessments.

Adverse events must be recorded under the signs, symptoms, or diagnosis associated with them, accompanied by the following information (as far as possible) (if the event is serious refer to Section 10.1.2):

- 1. The severity grade:
 - mild: usually transient in nature and generally not interfering with normal activities
 - moderate: sufficiently discomforting to interfere with normal activities
 - severe: prevents normal activities
- 2. Its relationship to the study treatment. If the event is due to lack of efficacy or progression of underlying illness (i.e. progression of the study indication) the assessment of causality will usually be 'Not suspected.' The rationale for this guidance is that the symptoms of a lack of efficacy or progression of underlying illness are not caused by the trial drug, they happen in spite of its administration and/or both lack of efficacy and progression of underlying disease can only be evaluated meaningfully by an analysis of cohorts, not on a single patient.
- 3. Its duration (start and end dates or ongoing) and the outcome must be reported.

- 4. Whether it constitutes a SAE (see Section 10.1.2 for definition of SAE) and which seriousness criteria have been met.
- 5. Action taken regarding with study treatment.

All AEs must be treated appropriately. Treatment may include one or more of the following:

- Dose not changed
- Dose reduced/increased
- Drug interrupted/permanently discontinued
- 6. Its outcome

Conditions that were already present at the time of informed consent should be recorded in medical history of the patient.

Adverse events (including lab abnormalities that constitute AEs) should be described using a diagnosis whenever possible, rather than individual underlying signs and symptoms.

Adverse event monitoring should be continued for at least 30 days following the last dose of study treatment.

Once an AE is detected, it must be followed until its resolution or until it is judged to be not recovered/not resolved (e.g., continuing at the end of the study), and assessment must be made at each visit (or more frequently, if necessary) of any changes in severity, the suspected relationship to the interventions required to treat it, and the outcome.

Information about adverse drug reactions for the investigational drug can be found in the product label.

Abnormal laboratory values or test results constitute AEs only if they fulfill at least one of the following criteria:

- they induce clinical signs or symptoms
- they are considered clinically significant
- they require therapy

Clinically significant abnormal laboratory values or test results must be identified through a review of values outside of normal ranges/clinically notable ranges, significant changes from baseline or the previous visit, or values which are considered to be non-typical in participant with the underlying disease. Alert ranges for laboratory and other test abnormalities are included in Appendix 1.

10.1.2 Serious adverse events

An SAE is defined as any adverse event [appearance of (or worsening of any pre-existing)] undesirable sign(s), symptom(s), or medical conditions(s) which meets any one of the following criteria:

- fatal
- life-threatening

Life-threatening in the context of an SAE refers to a reaction in which the patient was at risk of death at the time of the reaction; it does not refer to a reaction that hypothetically might have caused death if it were more severe (please refer to the ICH-E2D Guidelines).

- results in persistent or significant disability/incapacity
- constitutes a congenital anomaly/birth defect
- requires inpatient hospitalization or prolongation of existing hospitalization, unless hospitalization is for:
 - o routine treatment or monitoring of the studied indication, not associated with any deterioration in condition
 - o elective or pre-planned treatment for a pre-existing condition that is unrelated to the indication under study and has not worsened since signing the informed consent
 - o social reasons and respite care in the absence of any deterioration in the patient's general condition
 - o treatment on an emergency outpatient basis for an event not fulfilling any of the definitions of an SAE given above and not resulting in hospital admission
- is medically significant, e.g. defined as an event that jeopardizes the participant or may require medical or surgical intervention to prevent one of the outcomes listed above

Medical and scientific judgment should be exercised in deciding whether other situations should be considered serious reactions, such as important medical events that might not be immediately life threatening or result in death or hospitalization but might jeopardize the patient or might require intervention to prevent one of the other outcomes listed above. Such events should be considered as "medically significant." Examples of such events are intensive treatment in an emergency room or at home for allergic bronchospasm, blood dyscrasias, or convulsions that do not result in hospitalization or development of dependency or abuse (please refer to the ICH-E2D Guidelines).

Any suspected transmission via a medicinal product of an infectious agent is also considered a serious adverse reaction.

All reports of intentional misuse and abuse of the product are also considered SAE irrespective if a clinical event has occurred.

10.1.3 SAE reporting

To ensure patient safety, every SAE, regardless of causality, occurring after the patient has provided informed consent and until 30 days after the last study visit must be reported to local Novartis Patients Safety within 24 hours of learning of its occurrence. Detailed instructions regarding the submission process and requirements are to be found in the investigator folder provided to each site.

Screen failures

A screen failure occurs when a patient who is screened but is not treated or randomized. SAEs occurring after the patient has provided informed consent until the time the patient is deemed a screen failure must be reported to Novartis.

Treated patients

SAEs collected between time patient signs ICF until 30 days after the patient has discontinued or stopped study treatment.

All follow-up information for the SAE including information on complications, progression of the initial SAE and recurrent episodes must be reported as follow-up to the original episode within 24 hours of the investigator receiving the follow-up information. An SAE occurring at a different time interval or otherwise considered completely unrelated to a previously reported one must be reported separately as a new event.

If the SAE is not previously documented in the Package Insert (new occurrence) and is thought to be related to the study treatment, a Chief Medical Office and Patient Safety (CMO & PS) Department associate may urgently require further information from the investigator for health authority reporting. Novartis may need to issue an IN to inform all investigators involved in any study with the same study treatment that this SAE has been reported.

If a SAE is unexpected, i.e., the event an adverse reaction, the nature or severity of which is not consistent with the applicable product information and is suspected to be related to the Novartis study drug, this event is considered a Suspected Unexpected Serious Adverse Reaction (SUSAR). SUSARs will be collected and reported to the competent authorities and relevant ethics committees in accordance with EU Guidance 2011/C 172/01 or as per national regulatory requirements in China.

Any SAEs experienced after the 30-day period after the last study visit should only be reported to the local Novartis Patient Safety if the Investigator suspects a causal relationship to study treatment.

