Information about common side effects already known about the investigational drug can be found in the label. This information will be included in the patient informed consent and should be discussed with the patient during the study as needed. Any new information regarding the safety profile of the investigational drug that is identified between label updates will be communicated as appropriate, for example, via an investigator notification (IN) or an aggregate safety finding. New information might require an update to the informed consent and then must be discussed with the patient. In the event of recollection of informed consent is needed, the Investigator may conduct the informed consent discussion remotely (e.g., telephone or video conference). Guidance issued by local regulatory bodies, and ECs/IRBs on this aspect prevail and must be implemented and appropriately documented (e.g., the presence of an impartial witness, sign/dating separate ICFs by trial participant and person obtaining informed consent, etc.).

Women of childbearing potential must be informed that taking the study treatment may involve risks to the fetus if pregnancy were to occur during the study and agree that in order to participate in the study they must adhere to the contraception requirements.

Male patients must be informed that if a female partner becomes pregnant while he is enrolled in the study, contact with the female partner will be attempted to request her consent to collect pregnancy outcome information.

8 Visit schedule and assessments

The Assessment Schedule (Table 8-1) lists all of the assessments when they are performed. All data obtained from these assessments must be supported in the patient's source documentation.

Patients should be seen for all visits/assessments as outlined in the assessment schedule (Table 8-1) or as close to the designated day/time as possible. Missed or rescheduled visits should not lead to automatic discontinuation.

Patients who discontinue from the study treatment are to complete the end of treatment visit as soon as possible, and attend the follow-up visits as indicated in Table 8-1.

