9.1 Discontinuation and completion

9.1.1 Study treatment discontinuation and study discontinuation

Discontinuation of study treatment for a patient occurs when study treatment is stopped earlier than the protocol planned duration, and can be initiated by either the patient or the investigator.

The investigator must discontinue study treatment for a given patient if, he/she believes that continuation would negatively impact the patient's well-being.

Discontinuation from study treatment is required under the following circumstances:

- 1. Patient/guardian decision
- 2. Pregnancy
- 3. Use of prohibited treatment as per recommendations in the prohibited treatment section
- 4. ACEI/ARBs daily dosage below guided dosage last for 1 month
- 5. Any situation in which study participation might result in a safety risk to the patient
- 6. Withdrawal of informed consent

Study treatment may be discontinued at the investigator's discretion if any of the following occurs:

- 1. Any severe, or suspected AE, that may jeopardize patient well-being, if the study drug is continued
- 2. Suspected occurrence of angioedema
- 3. Serum potassium >6.0 mmol/L at follow Visit
- 4. Any laboratory abnormalities that in the judgment of the investigator, taking into consideration the patient's overall status, prevents the patient from continuing participation in the study

If discontinuation of study treatment occurs, the Investigator should make a reasonable effort to understand the primary reason for the patient's premature discontinuation of study treatment and record this information.

Patients who discontinue study treatment or who decide they do not wish to participate in the study further should NOT be considered withdrawn from the study UNLESS they withdraw their consent (see withdraw of informed consent section). Where possible, they should return for the assessments indicated in the assessment schedule. If they fail to return for these assessments for unknown reasons, every effort (e.g. telephone, email, letter) should be made to contact the patient/pre-designated contact as specified in the lost to follow-up section. This contact should preferably be done according to the study visit schedule. Patients are to be discontinued from the study treatment if patient has not received the study treatment for > 14 days.

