12.5.3 Safety endpoints

For all safety analyses, the SAF will be used and there will be no formal statistical inference analysis. All listings and tables will be presented by treatment group.

Safety summaries (tables and figures) include only data from the on-treatment period with the exception of baseline data which will also be summarized where appropriate (e.g. change from baseline summaries). In addition, a separate summary for death including on treatment and post treatment deaths will be provided. In particular, summary tables for AEs will summarize only on-treatment events, with a start date during the on-treatment period (treatment-emergent AEs).

Adverse events

All information obtained on AE will be displayed by treatment group and patient.

The number (and percentage) of patients with treatment-emergent AE (events started after the first dose of study medication or events present prior to start of double-blind treatment but increased in severity based on preferred term) will be summarized by treatment, primary system organ class, preferred term and maximum severity.

Separate summaries will be provided for study medication related AE, death, SAE, other significant AE leading to discontinuation and AE leading to dose adjustment.

The number and proportion of patients with AE as described in Section 10.1 will be summarized by treatment.

A patient with multiple AE within a primary system organ class is only counted once toward the total of the primary system organ class.

Adverse events which will be counted for a specific treatment period are those which are treatment-emergent. These events are those with an onset after the start of the treatment period, or which were present prior to the start of the treatment period but increased in severity, changed from being not suspected to being suspected of study drug relationship, or developed into SAEs after the start of the treatment period.

Vital signs

All vital signs data (see Section 8.4.2) will be listed by treatment group, patient, and visit/time and if ranges are available, abnormalities (and relevant orthostatic changes) will be flagged. Summary statistics will be provided by treatment and visit/time.

Clinical laboratory evaluations

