first ACEI/ARB administration and before ARNI administration. If the subject has not taken ARNI, TEAEs in the ACEI/ARB treatment group refer to adverse events that occur from the subject's first ACEI/ARB administration to 30 days after the subject's last ACEI/ARB administration. TEAEs in the ARNI treatment group refer to adverse events that occur from the subject's first ARNI administration to 30 days after the subject's last ARNI administration.

Pre-treatment events

Pre-treatment adverse events are defined as those that occur after the signing of the informed consent form and before the day of first administration of the investigational drug.

Drug-related adverse events (adverse reactions)

An adverse drug reaction (ADR) is a toxic and adverse reaction to a drug. An ADR indicates that there is at least a reasonable likelihood of a causality between the drug and an adverse event. In this study, the causality between an adverse event and the investigational drug is judged according to "suspected" and "not suspected". "Suspected" adverse events are judged as adverse reactions. If the event is due to lack of efficacy or progression of underlying illness (i.e. progression of the study indication), the assessment of causality will usually be 'Not suspected.'

AEs leading to death

Adverse events leading to death will be recorded by the investigator on the CRF Adverse Events Form. In addition, there is a specialized CRF to record deaths.

Serious adverse events

SAEs will be collected between time patient signs ICF until 30 days after the patient has discontinued or stopped study treatment. An SAE is defined as any adverse event [appearance of (or worsening of any pre-existing)] undesirable sign(s), symptom(s), or medical conditions(s) which meets any one of the following criteria:

- fatal
- life-threatening

Life-threatening in the context of an SAE refers to a reaction in which the patient is at risk of death at the time of the reaction; it does not refer to a reaction that hypothetically might have caused death if it is more severe.

- results in persistent or significant disability/incapacity
- constitutes a congenital anomaly or birth defect
- requires inpatient hospitalization or prolongation of existing hospitalization, unless hospitalization is for:
 - routine treatment or monitoring of the studied indication, not associated with any deterioration in condition.

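### Protocol 10.1.3 gives two end dates for SAE reporting; for patients who stop treatment early but stay in follow-up they differ by up to about 12 months, and the SAP carries only the shorter one

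*Protocol*

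**What the plan says.** Protocol 10.1.3 (SAE reporting) states the window three times.

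- The opening sentence covers every SAE regardless of causality: those "occurring after the patient has provided informed consent and until 30 days after the last study visit must be reported".
- The paragraph on treated patients says: "SAEs collected between time patient signs ICF until 30 days after the patient has discontinued or stopped study treatment".
- The closing paragraph returns to the visit anchor and only then narrows the duty to events with suspected causality: "Any SAEs experienced after the 30-day period after the last study visit should only be reported to the local Novartis Patient Safety".

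SAP 4.2.2 takes over the treatment-stop version alone: "SAEs will be collected between time patient signs ICF until 30 days after the patient has discontinued or stopped study treatment".

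Other sections decide whether the difference matters.

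- Protocol 9.1.1 says that patients who stop study treatment "should NOT be considered withdrawn from the study UNLESS they withdraw their consent". It lists AE/SAE among the minimum data to collect after discontinuation and sets no 30-day limit.
- The introduction to Protocol 8 says that such patients are to complete an end-of-treatment visit and "attend the follow-up visits as indicated in Table 8-1".
- Protocol 9.3 places a safety call 30 days after the last dose and asks for SAEs in that period to be reported under 10.1.3.
- Protocol 12.5.3 limits the safety summaries to the on-treatment period, but adds that "a separate summary for death including on treatment and post treatment deaths will be provided". SAP 7.5.2 plans the same.

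**The concern.** A patient who stops treatment at Month 3, stays on the visit schedule and has an SAE at Month 8 falls under two rules. The opening sentence of 10.1.3 makes the event reportable whatever its cause. The treated-patients sentence closes collection at about Month 4. The closing paragraph does not resolve this, because its suspected-only regime starts 30 days after the last visit. If the treated-patients sentence governs, the months in between are outside collection and also outside the suspected-only regime, so they have no workable rule.

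What is at stake is consistent safety data on patients who come off ACEI/ARB or ARNI early, who plausibly include those with intolerance or worsening disease. Sites that read 10.1.3 differently would send different sets of events to the sponsor's safety database. The SAE review subgroup in Protocol 8.5 works from the aggregated SAE data and would inherit that unevenness.

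**Working it through.** The documents give no figure for this gap, so there is nothing to reproduce. The check is date arithmetic.

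**Inputs**
- Last scheduled visit: Visit 7 at Month 12, window ± 2 weeks (Protocol Table 8-1).
- Planned treatment: 6 + 6 = 12 months (Protocol 6.1.5). The protocol glossary counts the control drug as study treatment, so stopping is possible from the first days of the ACEI/ARB period.
- Assumptions: treatment starts at about Month 0; 1 month = 365.25/12 = 30.44 days.

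**Formula**

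Let V be the day of the last visit and S the day treatment stops.
- End under the last-visit rule: V + 30.
- End under the treatment-stop rule: S + 30.
- Gap = (V + 30) − (S + 30) = V − S.

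The 30 days cancel, so the gap is the whole interval from stopping treatment to the last visit.

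**Results, last visit at nominal Month 12 (day 365.25)**

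| Treatment stops | Last-visit rule ends (day) | Treatment-stop rule ends (day) | Gap (days) | Gap (months) |
|---|---|---|---|---|
| Day 1 | 395 | 31 | 364 | 12.0 |
| Month 1 | 395 | 60 | 335 | 11.0 |
| Month 3 | 395 | 121 | 274 | 9.0 |
| Month 6 | 395 | 213 | 183 | 6.0 |
| Month 9 | 395 | 304 | 91 | 3.0 |
| Month 12 | 395 | 395 | 0 | 0 |

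**Effect of the visit window**
- Stop on day 1: the gap is 350 days (11.5 months) if the last visit is two weeks early and 378 days (12.4 months) if it is two weeks late.
- Completer who stops at nominal Month 12: the gap is −14 to +14 days. With an early final visit, the treatment-stop rule is the longer one by up to two weeks.

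**Which date fits the rest of the protocol**

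The last-visit anchor appears twice in 10.1.3. It agrees with section 8 (continued visits) and with 9.1.1 (not withdrawn; AE/SAE collected after discontinuation). The treatment-stop anchor appears in one sentence of 10.1.3 and in SAP 4.2.2, and 9.3 also counts its reporting period from the last dose. Protocol 10.1.1 asks for AE monitoring for at least 30 days after the last dose. That is a minimum and fits either reading.

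**The case against.** The case for treating this as minor has real substance.

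- **Events are not simply lost.** Table 8-1 collects adverse events and hospital admission data at every visit, and 9.1.1 requires AE/SAE even at abbreviated contacts. An SAE at Month 8 in a patient who stopped at Month 3 should still reach the study record. What is ambiguous is chiefly whether it is reported as an SAE. This stands.
- **The wide rule is the mandatory one.** The opening sentence is phrased as an obligation and the closing paragraph repeats its anchor, whereas the treated-patients line is a fragment. Sites are also referred to an investigator folder that is not among the documents. Under-reporting that varies by site is therefore a possibility and has not been shown. This stands too, but it does not explain why the SAP adopts the narrower date.
- **The effect on the SAP tables is small.** They are on-treatment by design, and SAP 7.5.2 lists all SAEs, so a later SAE that was collected would appear in a listing. This also stands.

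Two stronger readings are tempting but unsupported.

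- A reader might infer that the post-treatment death summary cannot be relied on. SAP 4.2.2 mentions a dedicated CRF for deaths, so deaths have a route outside the SAE window. The time span of that form is not stated, so the inference is unproven.
- A reader might size the gap from the 20% dropout rate: 0.20 × 219 = about 44 patients, and 44 × 6/12 = 22 patient-years if they stopped at Month 6 on average. That rate is a sample-size allowance for a paired analysis of complete cases. The gap exists only for patients who stop the drug and remain in follow-up. Some routes off treatment also end participation, such as dose limiting toxicity (6.5.2), ablation (6.2.1) and withdrawal of consent (9.2). The documents give neither the number who stay nor their stopping times.

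**Conclusion.** The contradiction is real and should be corrected. One section sets two incompatible end dates for SAE reporting, and the SAP has taken up only the shorter one. It is an internal inconsistency rather than a design choice.

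The discrepancy per patient equals the time from stopping treatment to the last visit. The maximum is about 12 months (11.5 to 12.4 with the visit window). Completers have none beyond the two-week window, and patients who leave the study when treatment stops are not affected. These figures assume treatment starts at about Month 0 and that the patient stays on the visit schedule to Month 12.

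The number of SAEs affected cannot be derived from the documents. The conclusion is limited to a risk of inconsistent SAE reporting to the safety database and to the SAE review subgroup. It does not extend to a demonstrated loss of events or deaths.

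**What to change.** Set one SAE end date and use it in three places: the treated-patients paragraph of Protocol 10.1.3, Protocol 9.3, and SAP 4.2.2. The last-visit date already in 10.1.3 is the one consistent with Protocol 8 and 9.1.1. Wording it as the later of 30 days after the last dose and 30 days after the last study visit also covers a completer whose final visit falls early. Protocol 9.3 must be included, because its safety call and the SAE reporting for that period are counted from the last dose. The call can stay where it is if the text says that SAE reporting continues to the common end date.

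In SAP 7.5.2, keep the on-treatment tables unchanged and add one separate summary of SAEs and deaths occurring after the on-treatment window. SAP 4.2.2 should also state the period that the death CRF covers.

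The cost is a few sentences in each document, one extra table, and somewhat more SAE forms for patients who are already being followed.
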